2.1.2 Visit Windows

The study visits can be obtained from the eCRF and need not be derived programmatically. The visits will be displayed as: Screening, Day 1 (Baseline), Day 2, ... Day 14, Day 15, Day 30, Day 45, Day 60, Day 75, Day 90/End of treatment (EOT).

Results from unscheduled visits will not be included in table summaries. These values will only be presented in the listings.

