- 7. Patient, born to a symptomatic mother diagnosed with COVID-19 at the time of birth or before birth;
- 8. Patient has received a diagnosis of COVID-19 (diagnosis <2 months prior and/or symptoms have not resolved);
- 9. Female patients who are pregnant. Note: All female patients ≥12 years of age must have a negative urine human chorionic gonadotropin (hCG) pregnancy test at screening. For female patients <12 years of age, a urine hCG test at screening will be performed at the discretion of the investigator based on childbearing potential.

Test Product: Clinolipid (lipid injectable emulsion, USP) 20%

Reference Therapy: Intralipid (lipid injectable emulsion, USP) 20%

Mode of Administration: The dosing schedule is the same for each of the injectable lipid emulsions (ILEs), Clinolipid and Intralipid (control).

Table 1. Dosing Schedule for Intravenous Lipid Emulsions (g/kg/d of lipid) ^a				
	Day 1 of PN ^b (g/kg/day)	Targeted daily advancement rate (g/kg/day)	Maintenance ^c (g/kg/day)	Maximum (g/kg/day)
Preterm infants	1	1	2.5 to 3	3
Term infants (0-<1y)	1	1	2.5 to 3	3
Children (1-<10y)	1	1	2 to 3	3
Adolescents (10-<18y)	1	1	1 to 2	3

^a Daily administration over 20-24 hours

- ^b Randomization is recommended within 24 hours of signing consent but must occur within 3 days of signing consent. If patient is not randomized within 24 hours of informed consent, patient should be started on standard of care ILE on Day 1 of PN and transitioned to study drug once randomization has occurred.
- ^c Unless there is a clinical reason to decrease the dose in the opinion of the Investigator

Duration of Treatment: from 7 days, up to 90 days

Statistical Methods:

Determination of Sample Size:

The sample size of 100 patients (50 in each of the 2 treatment groups: Clinolipid vs Intralipid), including neonates, is based on the feasibility of timely enrollment of patients for generating reference data and summary descriptive statistics, rather than on a formal power calculation.

Analysis Sets:

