7.2.3 Standard-of-Care Procedures

The following procedures will be performed at intervals determined by the SOC at each investigational site (refer to Appendix 1, Schedule of Events Table):

- Laboratory evaluations including:
 - hematology complete blood count
 - chemistry basic metabolic panel and electrolytes
- Diagnosis of neonatal morbidities including bronchopulmonary dysplasia (BPD), retinopathy of prematurity (ROP), intraventricular hemorrhage (IVH), periventricular leukomalacia (PVL), necrotizing enterocolitis (NEC), and late-onset sepsis in enrolled premature infants born at 24 to <37 weeks of gestation up to 1 month CA with a birth weight ≥750g.

7.2.4 Days 15, 30, 45, 60, 75 and 90 or End of Study Treatment Procedures

The Study Treatment Period starts when the patient receives study treatment. End of study treatment is defined as the last day of PN with Intralipid or Clinolipid; maximum 90 days of study treatment is allowed.

The following procedures will be performed approximately every 15 days ± 2 days for patients continuing on PN (days 15, 30, 45, 60, 75 and 90) and within ± 2 days of the last day of study treatment (maximum 90 days on either Clinolipid or Intralipid) whenever that occurs:

- Physical examination including weight, length or height (and head circumference for infants <1 year of age)
- Vital signs
- Concomitant medications
- Concomitant procedures
- AEs
- Laboratory evaluations including:
 - Hematology parameters
 - Serum chemistry parameters
 - Hepatic integrity parameters
 - Total and direct bilirubin
 - Triglyceride levels
 - FA profile
 - Holman Index
 - Phytosterol, cholesterol, and squalene levels

In addition, the following data will be collected at end of study treatment:

 Diagnosis of neonatal morbidities including bronchopulmonary dysplasia (BPD), retinopathy of prematurity (ROP), intraventricular hemorrhage (IVH), periventricular leukomalacia (PVL), necrotizing enterocolitis (NEC), and lateonset sepsis in enrolled premature infants born <37 weeks of gestation up to 1 month CA.

After end of study treatment (maximum of 90 days), the patient will receive nutritional intervention as prescribed by their healthcare provider as SOC if PN is still required.

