Appendix 1 Schedule of Events Table

Evaluation	Evaluation Screening Baseline ^a Dai		Daily	Study Treatment Day (every 15 days ±2 days)					End of Study Treatment ^o
				15	30	45	60	75	or Day 90 (± 2 days)
Informed consent / assent (as applicable)	X								
Confirm eligibility	X								
Randomization ^b	Х								
Demographics ^c	Х								
Medical history including diagnosis for requiring PN	Х	Х							
Physical examination including length or height and head circumference	X	Х		X	X	X	Х	X	Х
Body weight ^d	Х	Х	Х	Х	Х	Х	Х	Х	Х
Vital signs ^e	Х	Х	Х	Х	Х	Х	Х	Х	Х
Diagnosis of neonatal morbidities ^f									Х
Laboratory Evaluations									
Hematology and serum chemistry	Х	Х	Standard-of-Care and every 15 days ± 2 days						
Triglyceride levels	X	Х	Standard-of-Care and every 15 days ±2 days						
Hepatic function tests	Х	Х	Stand	ard-o	f-Car	e and	ever	y 15 a	days ±2 days
Fatty acid profile and Holman Index ^g		Х		Х	Х	Х	Х	Х	Х
Genetic polymorphism sample (buccal swab) ^h		Х							
Phytosterol, cholesterol, and squalene levels ⁱ		Х		Х	Х	Х	х	Х	Х
Human chorionic gonadotropin (hCG) ^j	X								
Nutritional Intake									
PN lipid intake ^k		X	X	Х	Χ	Χ	Х	Х	X
Other macronutrient PN intake		Х	Х	Х	Х	Х	Х	Х	Х
Breast milk intake ¹	X	Х	Х	Х	Х	Х	Х	Х	Х
Enteral formula intake	X	Х	Х	Χ	Χ	Х	Χ	Х	X

Evaluation	Screening Baseline ^a		Daily	Study Treatment Day (every 15 days ±2 days)				End of Study Treatment ^o	
				15	30	45	60	75	or Day 90 (± 2 days)
Oral food intake	Х	Х	Х	Х	Х	Х	Х	Х	Х
Concomitant medications / nutritional supplements ^m	Х	Х	Х	Х	Х	Х	Х	Х	Х
Concomitant procedures	Х	Х	Х	Х	Х	Х	Х	Х	Х
Adverse events ⁿ	Х	Х	Х	Χ	Χ	X	Χ	Χ	Х

PN=parenteral nutrition

^a Baseline evaluations should be done \leq 24 hours before first study treatment administration, however, baseline laboratory assessments may be done within ±24 hours of first study treatment administration. Baseline tests need not be repeated if within 24 hours of screening sampling. Buccal swabs can be collected at any time before the end of study treatment.

^b Randomization is recommended within 24 hours of signing consent but must occur within 3 days of signing consent (section 7.1)

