1.5.1 Definition of Analysis Populations

Full analysis set (FAS): all patients who are randomized to receive either Clinolipid or standard of care soybean oil-based lipid emulsion (Intralipid) and have received at least one randomized study treatment. This dataset will follow the intent-to-treat principle and will analyze patients by planned randomized arm.

Per protocol set (PPS): all patients in the FAS who have Holman Index measurements taken at baseline and at least 1 other timepoint post-baseline, who have received a minimum of 7 days of ILE treatment, and are without a major protocol violation (i.e. violation that potentially impacts the primary endpoint).

Deviations that could be considered for exclusion in a PP analysis

- Randomization or treatment errors
- Investigational product not handled properly
- Key exclusion criteria such as:
 - Patients with liver disease including cholestasis
 - Patients with severe hyperlipidemia or severe disorders of lipid metabolism
 - Patients who are unable to tolerate necessary laboratory monitoring
 - Patient requires or is expected to require propofol for sedation

Deviations that should **not** lead to exclusion of data in a PP analysis

- Patients who violate inclusion/exclusion criteria relating to patient safety
- Missed informed consent signature/date
- Any deviation that does not directly impact the primary endpoint

Safety analysis set (SS): the set of all patients who have been administered study treatment (Clinolipid or Intralipid). Patients will be analyzed according to treatment received.

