2.4.1.2 Analysis of Primary Endpoint

Holman index scores will be summarized descriptively by timepoint per treatment group using n, mean, standard deviation, minimum, Q1, median, Q3, and maximum.

The frequency and percentage of patients at risk of developing EFAD (Holman Index 0.2-0.4) as well as those who developed EFAD (Holman Index >0.4) will be summarized by timepoint and at the maximum by treatment group. The denominator for the percentage of patients will be the number of patients in the population who had at least one post-baseline Holman Index measurement available. The incidence rate (per 100 patient days) of EFAD will also be calculated per treatment group.

If there are more than 5 cases of EFAD per arm, then time to develop EFAD will be analyzed using survival analysis approach (cumulative incidence), and the mean, standard error, Q1, median, Q3, minimum, and maximum for each treatment group will be displayed, where calculable. A cumulative incidence plot will also be produced. If there are less than 5 cases of EFAD in each treatment arm, then time to developing EFAD will be summarized descriptively by treatment group using n, mean, standard deviation, minimum, Q1, median, Q3, and maximum. If no events occur, then time to EFAD will not be calculated.

A spaghetti plot consisting of Holman index values over time will be produced with one line representing each patient, and different types of lines or symbols (e.g. solid and dashed) representing each treatment group. Two bolded lines will be added at y=0.2 and y=0.4 to represent the bounds for being at risk of EFAD and developing EFAD.

As a supportive analysis to the primary endpoint, the following will be analyzed:

• FA profiles will be summarized using descriptive statistics (number of patients, mean, standard deviation, median, minimum, and maximum) in each of the 2 treatment groups (Clinolipid vs Intralipid), as well as descriptive statistics of genetic polymorphisms in the FADS1 and FADS2 genes for the patients with buccal swabs with the 5 highest and 5 lowest arachidonic acid values in each treatment group.

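### By-visit tables put Day 90 and end of treatment in one column, so its last values mix exposures from about a week or less up to 90 days

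*SAP*

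**What the plan says.** SAP 2.1.2 (Visit Windows) ends its list of displayed visits with one category, "Day 90/End of treatment (EOT"). On the source of the labels it says "The study visits can be obtained from the eCRF and need not be derived programmatically". It has no rule based on actual study day, and it sends unscheduled results to the listings only.

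The schedule in Protocol Appendix 1 has the matching single column, end of study treatment "or Day 90 (± 2 days"). Protocol 7.2.4 places that visit "within ± 2 days of the last day of study treatment (maximum 90 days on either Clinolipid or Intralipid) whenever that occurs". The planned range in the protocol synopsis is "Duration of Treatment: from 7 days, up to 90 days". The full analysis set in SAP 1.5.1 asks only that randomized patients "have received at least one randomized study treatment", so a last sample can fall before Day 7.

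These labels drive several tables. Under SAP 2.4.1.2 the Holman Index is described by timepoint, and the at-risk and EFAD frequencies "will be summarized by timepoint and at the maximum by treatment group". Hepatic tests (SAP 2.4.2.3) and laboratory results (SAP 2.5.2.5) are summarized by measurement time or visit, and growth (SAP 2.4.3.5) about every 15 days. Nothing in either document separates a true Day 90 value from an early EOT value, moves an early EOT value to another visit, or reports the day on which the EOT sample was drawn.

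**The concern.** A table by visit is read as a table by time on treatment. Here the last column is not a time. A value from a child who left parenteral nutrition after a week and one from a child treated for three months are summarized together under a label that includes Day 90. If the Holman Index drifts with exposure, the drift is diluted in the column where a reader would look for it.

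The trial is purely descriptive: SAP 1.4.2 plans no hypothesis test. Tables like these are much of what it will deliver.

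The mix of exposures also need not be the same in both arms. Protocol 6.14 discontinues Clinolipid patients who must receive Intralipid as rescue and asks for EOT procedures at discontinuation. Their last value then enters this column on whatever day that happens. The documents do not say how often to expect this.

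**Working it through.** The plan has no figure to reproduce. The sample size (50 per arm) rests on feasibility, and no distribution of treatment duration is given. The check has three parts.

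**1. Where a patient's values go**

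- Last treatment day 7: no Day 15 sample is due. The EOT sample is the only scheduled post-baseline Holman value, shown under Day 90/EOT.
- Last treatment day 20: the Day 15 value stays in the Day 15 column. The second value, from about Day 20, goes to Day 90/EOT.
- Last treatment day 90: the final value goes to Day 90/EOT.

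The first and third patients average to (7 + 90)/2 = Day 48.5 in that column. The Day 15 visit has a ±2-day window, so it opens on Day 13. That is why the first pattern applies to stops before about Day 13. It holds strictly for the Holman Index; local laboratory tests are also drawn at standard-of-care intervals.

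**2. How much of the column this could be**

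Assumption, not from the documents: treatment lasts 7 days plus an exponential time, capped at Day 90, and every patient has an EOT sample. With median M:

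- m = (M − 7)/ln 2, and S(t) = exp(−(t − 7)/m)
- share whose only scheduled post-baseline Holman value is in the column = 1 − S(13)
- share of the column that is a true Day 88-90 value = S(88)
- mean last treatment day = 7 + m(1 − exp(−83/m))

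For M = 14: m = 7/0.693 = 10.1; 1 − exp(−6/10.1) = 0.45; exp(−81/10.1) is about 0.0003; mean day = 17.1.

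For M = 45: m = 38/0.693 = 54.8; 1 − exp(−6/54.8) = 0.10; exp(−81/54.8) = 0.228; mean day = 49.8.

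| Assumed median (days) | Only post-baseline value in the column (of 50) | True Day 88-90 values (of 50) | Mean last treatment day |
|---|---|---|---|
| 10 | 37.5 (75%) | 0.0 (0%) | 11.3 |
| 14 | 22.4 (45%) | 0.0 (0%) | 17.1 |
| 21 | 12.9 (26%) | 0.9 (2%) | 26.9 |
| 30 | 8.3 (17%) | 4.4 (9%) | 37.5 |
| 45 | 5.2 (10%) | 11.4 (23%) | 49.8 |

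Even at a 45-day median, about 77% of the values (100 − 23) are not near Day 90.

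**3. Growth rates**

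The from-baseline formulas in SAP 2.4.3.5 divide by the visit day X (or X/7), and X is not defined for an EOT visit. If a programmer took X = 90 from the label for a patient who stopped on Day 7, the daily gain would be understated 90/7 = 12.9-fold. The SAP does not instruct this; it leaves it open.

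**The case against.** The best defence is that the main results do not use visit labels, and it stands. Under SAP 2.4.1.1 a patient counts as EFAD on any value above 0.4 during treatment, time to EFAD uses the laboratory date, and the incidence rate uses actual dates. SAP 2.4.1.2 adds a row at the maximum and a plot of each patient's Holman Index over time. A reader might infer that the primary EFAD proportion is distorted, and these rules do not support that.

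A reader might also infer that early stoppers disappear from the results. They do not. They remain in the Day 90/EOT column, the maximum row, the incidence rate, the time-to-event analysis and the listings. Patients who stop later stay in every 15-day column they reached. That the Day 30 to 75 columns contain only patients still on treatment follows from the sampling schedule, and no relabelling will change it.

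Nor do the documents show that a patient who stops on, say, Day 16 has the only sample stored as Day 90/EOT. That patient passes through the Day 15 window. A sample taken then satisfies both visit definitions, and the eCRF convention is not in the documents.

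Finally, pooling across durations is intended where the target is end of treatment: the hepatic shift tables (SAP 2.4.2.3) and the sterol summaries (SAP 2.4.2.4). Total treatment days are summarized by arm (SAP 2.5.2.6 and 2.5.2.7), but that summary is not tied to the EOT column.

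What none of this answers is the by-visit tables themselves.

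**Conclusion.** The defect is real but limited to display. In the by-timepoint summaries of the Holman Index, EFAD and at-risk frequencies, laboratory tests and growth, the final column mixes exposures from about 7 days or less up to 90 days under a Day 90 label, with nothing to show the actual day.

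That conclusion comes from the text alone. Its size does not: the percentages depend on the assumed shape and median of treatment duration, and should be quoted only as a range. Stops before Day 7, which the full analysis set allows, are outside the model. The correction is worth making because it is cheap and these tables would otherwise mislead, but the headline EFAD results can be read as planned.

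**What to change.** In SAP 2.1.2:

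- Show EOT as its own row, named as the last on-treatment value, with the median and range of actual study day by arm. Keep Day 90 for samples on Day 90 ±2.
- In by-timepoint tables, assign an EOT sample to a nominal visit only if its actual study day lies within that visit's ±2-day window and no scheduled sample exists there. Otherwise show it only in the EOT row. A general nearest-visit rule would be too loose: it would relabel a Day 3 or Day 12 sample as Day 15, and would leave two values in one window for a patient sampled on Day 15 and again at a Day 18 stop.

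In SAP 2.4.3.5, use the actual study day for X in the growth-rate formulas at EOT.

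The cost is one derived variable; the analysis already uses laboratory dates, so no new data are needed. The true Day 90 row will probably be small, between 0 and about 11 of 50 per arm under the assumptions above. That is a fair picture of how much the trial can say about Day 90.

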6.7.2.3 Liver function tests

Blood samples for liver function tests will be collected from all patients enrolled in the study. Blood samples should be collected at Screening/Baseline and then during SOC blood draws as well as on an approximately 15-day basis (ideally, blood should be collected at approximately the same time on each day the sample is to be drawn).

Samples will be processed and tested as per the investigational site's standard laboratory procedures.

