6.8.3 Holman Index >0.4

Patients with Holman index >0.4 will be considered as biochemical EFAD. It will be confirmed in the context of low LA, low ARA, and high eicosatrienoic acid (Mead acid).

Clinical EFAD is diagnosed in the presence of any clinical features of EFAD (dermatitis, diarrhea, perianal irritation, growth and development failure, recurrent infections, irritability, and/or poor wound healing).

The management of these patients includes the assessment, the record, and the increase of LA intakes until the Holman Index normalizes and clinical features, if present, disappear.

The daily monitoring of LA intakes, and the approximately every 15 day monitoring of LA and ARA levels and Holman Index will persist until the Holman Index normalizes and clinical features disappear. If the Holman Index does not reduce to <0.4 or if it continues to increase, lipid intake will be further increased. The amount of the increase in LA intake should be determined by the clinician considering the clinical state of the patient and the safety of increasing the total lipid intake.

Some patients may have higher requirements for EFAs due to an underlying disease (e.g. high demand for growth and wound healing). Total parenteral lipid intake should usually remain below the maximum intake (Table 4, Dosing Schedule), which is an amount that is normally adequate for prevention of EFAD in all patients. The patient should receive the increased LA intake for at least 1 week prior to repeating the FA profile with the Holman Index assessments to allow time for the physiologic effects of the FA to occur.

When EFAD persists despite maximal lipid intake, the ILE should be unblinded. If the patient is receiving Clinolipid, the patient should be switched to Intralipid to allow for greater delivery of LA.

Additional LA intakes may be supplied via intravenous and/or enteral/oral routes.

If severe hypertriglyceridemia (triglycerides >400 mg/dL) develops, the cause should be investigated. If it is determined to be related to the ILE, lipid intake may be adjusted using the ILE with the higher relative content of LA.

If direct bilirubin increases above 2.5 mg/dL suggestive of cholestasis, a reduction of total lipid intake may be considered while continuing to provide adequate LA. The adequacy of LA intake needs to be confirmed by the unblinded pharmacist(s).

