2.4.1.1 Derivation of Primary Endpoint

The primary endpoint is the incidence of EFAD which is defined in the protocol and will be derived based on the Holman Index (Triene/Tetraene Ratio) provided by the central laboratory.

- Holman Index <0.2: normal EFA
- Holman Index 0.2 0.4: at risk for EFAD
- Holman Index >0.4: EFAD

A patient will be considered 'at risk for developing EFAD' if they have a Holman Index of 0.2 - 0.4 at any timepoint during the study treatment.

A patient will be considered as an incident of EFAD (the 'event') if they have a Holman Index >0.4 at any timepoint during the study treatment.

For time to EFAD Kaplan Meier analyses, the index time will be the start of treatment. The first incident of EFAD will be considered the event and will use the date of EFAD (date first lab with Holman Index >0.4 reported). Patients will be censored if they do not develop EFAD during their follow-up or if they die before developing EFAD at the time of their last Holman Index laboratory measurement. Time to EFAD will be calculated for each patient who develops EFAD as follows and standardized to days:

The incidence rate of EFAD (events per 100 patient days) will be calculated as the following per treatment group:

```
Number of patients developing EFAD * 100
Total patient days
```

The total number of patient days will be calculated per treatment group as follows:

$$\sum_{i=1}^{n} (Date of First EFAD Occurrence or End Date of Treatment)$$

- Start Date of Treatment)_i + 1

Where n is the total number of patients per treatment group. If a patient develops EFAD, then the date of first EFAD occurrence will be used, and if they do not, then end date of treatment will be used. If more than one instance of EFAD occurs, the patient will be counted once and the date of first occurrence will be used. This will then be standardized to days.

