2.4.2.1 Liver Disease, Including Parenteral-Associated Liver Disease

2.4.2.2 Parenteral Nutrition-Associated Liver Disease (PNALD)

2.4.2.2.1 Derivation of PNALD

PNALD will be determined by a direct bilirubin measurement $\geq 2 \text{ mg/dL}$ at any timepoint in the study.

Time to PNALD will be derived using the start of treatment as the index date and the date of developing PNALD as the event date. It will be calculated for each patient as follows (standardized to the number of days):

Date of PNALD - Start Date of Treatment + 1

Patients will be censored at the time of their last lab value if they do not develop PNALD. Each patient will have their person time (or total exposure to potentially develop PNALD) calculated in "patient days" as:

> Date of first occurrence of PNALD or End Date of Treatment - Start Date of Treatment + 1

If a patient develops PNALD, then date of first occurrence of PNALD will be used. If a patient does not develop PNALD, then end date of treatment will be used. If a patient has more than 1 lab indicating PNALD, they will only be counted once at the date of their first instance. For incidence rate calculations, the total person time per group will be the sum of all individual patient's person time in that group standardized to 100 patient days:

Incidence Rate of PNALD =
$$\frac{Total \# with PNALD * 100}{\sum_{i=1}^{n} Person Time}$$

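### SAP 2.1.2 keeps unscheduled results out of every table, which conflicts with PNALD and maximal liver values defined over all timepoints

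*SAP*

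**What the plan says.** SAP 2.1.2 (Visit Windows) names the visits used for display: Screening, Day 1, each of Days 2 to 14, then Days 15, 30, 45, 60, 75 and Day 90/end of treatment. Labels come from the eCRF: "The study visits can be obtained from the eCRF and need not be derived programmatically". It then states: "Results from unscheduled visits will not be included in table summaries". The next sentence confines these values to the listings.

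Other SAP sections work over all timepoints:

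- **2.4.2.2.1:** "PNALD will be determined by a direct bilirubin measurement" of 2 mg/dL or more, whenever in the study it occurs. Time to PNALD and person-time stop at the first such result.
- **2.4.2.2.2:** PNALD is tabulated by visit and at the post-baseline maximum, where one positive result at any time counts as yes.
- **2.4.2.3:** shift tables, days to maximum and the Hy's Law/eDISH plots use maximal values.
- **2.4.1.1:** "A patient will be considered as an incident of EFAD (the 'event') if they have a Holman Index >0.4 at any timepoint" while on study treatment.
- **2.6.2:** everything collected up to dropout goes into the analyses.

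On sampling, Protocol 6.7.2.3 says of liver tests: "Blood samples should be collected at Screening/Baseline and then during SOC blood draws as well as on an approximately 15-day basis". The Schedule of Events agrees. Protocol 7.2.4 sets the planned visits: "The following procedures will be performed approximately every 15 days ± 2 days for patients continuing on PN", with a further set within 2 days of the last treatment day.

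**The concern.** The general rule and the endpoint derivations cannot both be followed as written. A direct bilirubin of 2.4 mg/dL from a standard-of-care draw on Day 22 is a PNALD result under SAP 2.4.2.2.1. Day 22 is not a named visit, so if the eCRF labels the draw unscheduled, SAP 2.1.2 confines it to a listing.

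The outputs at stake are the PNALD table (14.3.6.1.1), the shift-to-maximum table (14.3.6.2.2) and days to maximum (14.3.6.2.3). Because SAP 2.1.2 says the values appear only in listings, the Hy's Law/eDISH figures are arguably affected too. Losses would push PNALD counts and peaks down. A missed case would also add person-time up to the end of treatment, lowering the incidence rate further.

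PNALD belongs to the first-listed secondary endpoint. The trial plans no hypothesis test, so the tabulated counts and rates are the result. Protocol 9.6.1.1 counts PNALD over the whole treatment period and 9.6.1.2 uses maximal values during the intervention. SAP section 3 declares no departure from either.

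**Working it through.** The plan has no figure to reproduce. The 50 per arm rests on feasibility, and no event rate or standard-of-care draw frequency is given. Spell lengths, weekly draws and PNALD risks below are assumptions.

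**1. Days with no planned visit.** The ±2-day windows around Days 15, 30, 45, 60 and 75 cover 5 × 5 = 25 days, and Days 88 to 90 add 3, so 28 in all. Of the 89 days from Day 2 to Day 90, 89 − 28 = 61 (69%) lie outside. If every draw on Days 2 to 14 takes its daily visit label, the remaining span is Days 15 to 90, or 76 days. The windows cover 3 + 4 × 5 + 3 = 26 of these and leave 50 (66%) outside.

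**2. Chance of missing a spell.** Suppose direct bilirubin is at or above 2 mg/dL for one spell of L days and only the 15-day draws count. The chance of missing it is 1 − L/15, and zero from L = 15. A simulation of 200,000 spells checked this, with onset uniform over Days 1 to 60, planned draws spread over ±2 days and treatment to Day 90. It was repeated with weekly standard-of-care draws added.

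| Spell (days) | Missed, 1 − L/15 | Detected, planned draws only | Detected, planned plus weekly |
|---|---|---|---|
| 3 | 80% | 19% | 54% |
| 5 | 67% | 33% | 81% |
| 7 | 53% | 47% | 100% |
| 10 | 33% | 67% | 100% |
| 14 | 7% | 92% | 100% |
| 21 | 0% | 100% | 100% |

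Two planned draws can be up to 15 + 2 + 2 = 19 days apart, so the zero at 15 days is exact only for draws on the nominal days. Spells of 14 and 21 days that the planned draws do catch are dated on average 4.0 and 4.6 days later than with weekly draws counted.

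**3. Effect on PNALD counts.** Take 50 per arm, 7-day spells and 47% detection. Expected tabulated cases are 50 × risk × 0.47, against 50 × risk with all draws counted. SAP 2.4.2.2.2 uses survival methods only with more than 5 cases per arm. The last two columns give the binomial chance that one arm has at least 6.

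| Assumed risk | Cases, all draws | Cases, planned only | More than 5, all draws | More than 5, planned only |
|---|---|---|---|---|
| 5% | 2.5 | 1.2 | 4% | 0.1% |
| 10% | 5.0 | 2.3 | 38% | 3% |
| 20% | 10.0 | 4.7 | 95% | 33% |

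These are upper-end figures. They assume that every draw between planned visits is dropped, including those on Days 2 to 14, and give no patient an early end-of-treatment sample.

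**4. EFAD.** Fatty-acid profiles have no standard-of-care draws in the Schedule of Events. An index of 0.2 to 0.4 is followed about every 15 days (Protocol 6.8.2), baseline EFAD likewise (6.8.4), and suspected EFAD is confirmed by planned profiles (6.8). The one off-schedule prompt is in 6.8.3: "The patient should receive the increased LA intake for at least 1 week prior to repeating the FA profile". It concerns patients already above 0.4. SAP 2.4.1.1 counts each patient once, at first occurrence, so losing a later repeat neither removes the event nor moves its date. Expected loss by this route is about zero.

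**The case against.** The strongest reply is that nothing need be lost. The Schedule of Events prescribes liver tests at standard-of-care times, so these draws are protocol-specified and may not be labelled unscheduled. Days 2 to 14 are named visits and can hold early draws. The exclusion sits under a visit-windows heading and can be read as governing by-visit display, while the specific PNALD and maximum rules, and SAP 2.6.2, point to using everything. Values also remain in the PNALD, hepatic and drug-induced liver injury listings (16.2.8.2.1 to 16.2.8.2.3) and in abnormal liver Listing 14.3.4.2.

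Much of this stands, and it makes the loss conditional. It does not remove the conflict. The SAP never says how a standard-of-care draw is labelled, gives no visit for one between the 15-day visits after Day 15, and writes the exclusion without exception. Listings do not produce the counts, rates or shift tables.

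Three stronger readings are tempting but unsupported:

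- **The primary endpoint is undercounted.** The repeat profile follows an event already counted, and other fatty-acid samples are planned.
- **Hy's Law peaks are certainly lost.** The first sentence of the rule concerns tables, whereas Hy's Law is assessed in figures. Only the listings-only sentence reaches them, and that is arguable.
- **Sicker patients lose the most data.** This is plausible, but the documents give no standard-of-care frequency, by severity or otherwise.

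**Conclusion.** The conflict is real for PNALD and maximal liver values. Followed literally, SAP 2.1.2 removes from the tables any standard-of-care liver result labelled unscheduled, against the SAP's own derivations and its statement on data use.

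The size is conditional on eCRF labelling, which the documents do not show. If all such draws were excluded, a 7-day spell would be missed about 53% of the time and a 10-day spell about 33%. From 15 days the nominal grid misses none, though onset may be dated late. The Day 2 to 14 visits and the end-of-treatment draw reduce these figures.

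For EFAD only the wording conflict between SAP 2.1.2 and 2.4.1.1 remains. It would matter only if an ad hoc sample outside the plan were the first to exceed 0.4.

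Should-fix, with moderate confidence.

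**What to change.** Amend SAP 2.1.2 in three steps:

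1. Limit the exclusion of unscheduled results to by-visit descriptive summaries.
2. State that every on-treatment result, whether scheduled, standard-of-care or unscheduled, feeds PNALD and EFAD status and date, person-time, post-baseline maxima, shift-to-maximum tables, days to maximum and Hy's Law peaks.
3. Add a rule assigning standard-of-care draws to visits for the by-visit tables, including which value is used when several fall near one visit.

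The cost is a few SAP sentences and a programming flag. No new data are needed.
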